10.7 Safety review committee

After each cohort, the Safety Review Committee will evaluate the safety, tolerability and PK up to 14 days of dosing with NT-814 to determine escalation to the next dose in Cohorts 2 and 3 and the doses for Cohorts 4 and 5 (if applicable). Safety data to be reviewed will include, but is not limited to, AEs, vital signs, Holter monitoring data and available laboratory parameters. This review must comprise complete data up to Day 15 from a minimum of 14 subjects per cohort. The Safety Review Committee will be comprised of the Principal Investigator, Medical Monitor, appropriate Sponsor and CRO representatives.

Following review of data from a cohort of subjects, the timing of assessments and/or blood samples may be adjusted for subsequent cohorts. Additional assessment or sampling times may be added if indicated by the data; however, the maximum blood volume taken from each subject will not exceed 500 ml.

In the event that study stopping criteria have not been met, but the Safety Review Committee do not feel that it is appropriate to escalate to the next planned dose, the subsequent Cohort may be dosed at any of the previous dose levels, in order to confirm safety and PK data for this dose.

In the case of any safety concern or any ambiguous data, during any one of the cohorts, either individual subjects or the entire cohort may be unblinded to enable decision making. In this eventuality a separate un-blinded Safety Review Committee will be used to maintain the integrity of following cohorts. Details will be outlined in the Safety Review Committee Charter.

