4 STUDY DESIGN

4.1 General

This is a multicenter, double-blind, randomized, placebo-controlled multiple ascending dose trial in postmenopausal women with vasomotor symptoms.

Subjects will be recruited into a maximum of 5 sequentially-dosed cohorts; Cohort 1 (50 mg NT-814), Cohort 2 (100 mg NT-814), Cohort 3 (150 mg NT-814), and, if needed, 2 further cohorts up to 400mg NT-814. Refer to [Figure 1](#) for the study design schematic.

For each cohort, subjects will enter a 4 week screening period to determine eligibility. Twenty eligible subjects will be randomized per cohort (15 active and 5 placebo).

During screening, each subject will be required to complete twice-daily diaries. Eligible subjects will demonstrate, at the baseline visit, an average 24-hour moderate to severe hot flash frequency of ≥ 7 and ≤ 20 , based upon the average daily frequency of all available readings (at least 4 days) in the final week of screening (Week -1). If, at the baseline visit, subjects have an average 24-hour hot flash frequency < 7 /day or > 20 /day, they will be discontinued from the study. In addition, subjects who have a change of $\geq 50\%$ in average 24-hour hot flash frequency between the first and second week of screening (i.e., Week -2 and Week -1) will also be discontinued. Subjects will also be provided with the continuous daily diary during screening and instructed to start completing this on the morning of Day -1 after waking, prior to admission to the clinic, and to continue to complete this throughout Day -1.

It may be necessary to extend a patient's screening period beyond 28 days (with the approval of the sponsor) when a subject is held over from one cohort to the next because the original cohort into which they would have been enrolled is complete. If this occurs, the following safety procedures must be repeated such that the most recent evaluation occurs within 28 days of the rescheduled randomization:

- Biochemistry and hematology
- Vital signs
- 12-lead ECG
- Physical examination

If the subject has completed (or partially completed) the screening twice daily Hot Flash Diary this must still be repeated and a new diary started on the new planned Day -15 and completed for the 2 weeks up to Day -2. Eligibility will be assessed on the repeated diary, not the initial one. If the subject had not started completing their screening diary at the time screening was put on hold, they will start this screening diary on the re-scheduled Day -15.

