4.4 Randomization and Treatment Assignments

Following screening and confirmation of eligibility, subjects in each cohort will be randomized on Day 1 in a 3:1 ratio to receive either NT-814 or placebo. The investigational medicinal

product (IMP) that each subject will receive will be allocated by an Interactive Web Response Services tool provided by the Clinical Research Organization on behalf of the Sponsor.

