8 STATISTICAL METHODS

8.1 General

The statistical analysis will be conducted following the principles specified in the International Council for Harmonization, formerly the International Conference on Harmonization, Topic E9 Statistical Principles for Clinical Trials (CPMP/ICH/363/96).

All statistical tabulations and analyses will be done using SAS[®], Version 9.3 or higher.

Unless otherwise noted, continuous variables will be summarized using number of non-missing observations, arithmetic mean, standard deviation (SD), median, minimum, and maximum; categorical variables will be summarized using the frequency count and the percentage of subjects in each category.

In the data listings, study day relative to first dose of study drug may be presented. Study day relative to first dose will be calculated as: event date – first dose date (+ 1 if event date \geq first dose date). That is, there is no Day 0.

Baseline will be the latest available measurement prior to the first study drug administration in the study, unless otherwise specified.

For safety summaries, the unscheduled and repeat assessments will not be summarized; however, all results will be included in the data listing.

All subject level data, including those derived, will be presented in the individual subject data listings.

Unless otherwise noted, the analyses will be done by treatment (50 mg NT-814, 100 mg NT-814, 150 mg NT-814, etc... (XX mg NT-814), Total NT-814 (if applicable), placebo). Data for the placebo subjects will be combined across cohorts prior to any summaries.

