8.10 Analysis of Efficacy Data

All efficacy analyses will be performed using the Full Analysis Set and are considered as exploratory. Any statistical hypothesis tests and/or CIs will be two-sided, using a type I error rate of 0.1. No adjustments will be made for multiplicity in this early phase study. An unstructured covariance matrix is planned for the analyses that use linear mixed-effects models. However, alternative covariance matrices may be used if the unstructured matrix causes model convergence issues.

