8.10.1 Twice Daily Hot Flash Paper Diaries

8.10.1.1 Frequency of Hot Flashes

Frequency by day

Daily (24-hour) frequency of hot flashes for Day Y will be equal to the number of hot flashes recorded on Day Y (day time hot flushes recorded in the evening + night time hot flushes recorded the following morning).

The daily frequency of mild, moderate, severe, moderate/severe, and total hot flashes will be summarized for each day. The mean (\pm SE) frequency of mild, moderate, severe, moderate/severe (moderate and severe combined), and total hot flashes will be displayed graphically by day (Day -8 onwards).

Average daily frequency by week

The average daily frequency of hot flashes for each of Week -1, Week 1, and Week 2 will be equal to the average of the daily frequency of hot flashes from Day -8 to Day -2 inclusive, from Day 1 to Day 7 inclusive, and from Day 8 to Day 14 inclusive, respectively.

The average daily frequency by week and the change from Week -1 (for Week 1 and Week 2) of mild, moderate, severe, moderate/severe, and total hot flashes will be summarized descriptively by treatment.

Statistical analysis

The analysis will test the treatment difference of change in the average daily frequency of moderate/severe hot flashes from Week -1 to each of Week 1 and Week 2.

The analysis will be based on a linear mixed-effects model with the change from Week -1 as a dependent variable, treatment, week, treatment-by-week interaction as fixed effects, subject as a random effect, and baseline (frequency of moderate/severe hot flashes at Week -1) and baseline-by-week interaction as covariates. Subjects dosed with placebo will be analyzed as a pooled group. An unstructured covariance matrix will be specified for the repeated measures at postdose timepoints for each subject. From this analysis, the least-squares (LS) mean and 2-sided 90% CIs will be calculated for the contrast “NT-814 versus placebo” for each treatment and each postdose week, separately.

Following is the SAS code for reference:

```
proc mixed data=dataset ;  
class TRT <50 mg NT-814, 100 mg NT-814, 150 mg NT-814, etc... , placebo> WEEK <1,2> USUBJID;  
model CHG = TRT WEEK TRT*WEEK BSL BSL*WEEK / s ddfm=kr;  
random USUBJID;  
repeated WEEK / type=un subject=USUBJID;  
lsmeans TRT*WEEK / cl diff alpha=0.1;  
run;
```

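### Each dose is compared with placebo pooled over all cohorts and no cohort term is fitted, so any cohort-wide shift would pass largely into that dose's estimate, and no planned summary would show it

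*SAP*

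**What the plan says.** SAP 4.4 states that "subjects in each cohort will be randomized on Day 1 in a 3:1 ratio to receive either NT-814 or placebo". SAP 4.1 gives 15 active and 5 placebo women per cohort, in at most five cohorts dosed one after another. The PK analysis plan (section 3) describes four cohorts, each at a different dose.

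For the analysis, SAP 8.1 says: "Data for the placebo subjects will be combined across cohorts prior to any summaries". In the twice-daily diary model (SAP 8.10.1.1), "Subjects dosed with placebo will be analyzed as a pooled group", and the reference code is "model CHG = TRT WEEK TRT*WEEK BSL BSL*WEEK / s ddfm=kr". The continuous diary model (8.10.2.1) and the LH model (8.10.4) have the same form with day in place of week. Severity, severity score, awakenings and skin conductance (8.10.1.2 to 8.10.1.4, 8.10.2.2, 8.10.3) follow by cross-reference. The by-timepoint ECG model in 8.11.7 also sets each dose against all placebo. None of these models has a cohort, period or site term.

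On error control, SAP 8.10 says "Any statistical hypothesis tests and/or CIs will be two-sided, using a type I error rate of 0.1" and "No adjustments will be made for multiplicity in this early phase study".

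**The concern.** The comparison that randomisation protects is between the 15 active and 5 placebo women of the same cohort. The planned contrast sets those 15 against every placebo woman in the trial. With four cohorts, 15 of the 20 comparators were not randomised alongside the active women; with five cohorts, 20 of 25. In the planned design each dose belongs to one cohort, so dose and cohort are separated only through the placebo women, and the model does not use them for that.

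The documents leave room for cohorts to differ:

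- Planned enrolment to completion runs from August to March at four centres (protocol synopsis).
- After a cohort is reviewed, "the timing of assessments and/or blood samples may be adjusted for subsequent cohorts" (protocol 10.7).
- Capsule number rises from one to three over Cohorts 1 to 3, and placebo is given in the same way (protocol 9.1), so expectation could differ by cohort in both arms on a self-reported outcome.

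A shift shared by both arms of a cohort could then look like a dose effect or a step in a dose response. Comparison with placebo on hot flash measures is a stated exploratory objective (SAP 3.2).

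**Working it through.** **Inputs.** From the documents: 15 active and 5 placebo women per cohort; K = 4 cohorts (PK analysis plan) or 5 (maximum in SAP 4.1); two-sided error rate 0.10. Assumed: the cohort ICC, meaning the between-cohort share of the variance in change after baseline adjustment. The documents give none, so a range is shown.

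**Step 1: share of a shift credited to the dose.** The contrast for cohort k's dose is the active mean of cohort k minus the mean of all 5K placebo women. If both arms of cohort k shift by d, the active mean moves by d and the pooled placebo mean by 5d/(5K) = d/K. The contrast moves by d(1 - 1/K): 0.75d for K = 4, 0.80d for K = 5. Every other dose's contrast moves by d/K in the opposite direction. Against concurrent placebo, the shift cancels.

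**Step 2: reproduce the plan's 10%.** At one post-dose time with complete data, the contrast is an analysis of covariance on baseline. Its variance, in residual-variance units, is V0 = 1/15 + 1/(5K), on 20K - K - 2 degrees of freedom. With no cohort effect the test has exactly its nominal 10% rate for either K.

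**Step 3: add a cohort effect.** Let r = ICC/(1 - ICC) be the cohort variance in residual-variance units. The true contrast variance becomes V1 = V0 + r(1 - 1/K). The residual variance the model estimates rises only slightly, by the factor f = 1 + 5r(K - 1)/df, because the only between-cohort spread it can see is among placebo women. The false-positive rate is P(|t| > t0.95 x sqrt(V0 f/V1)).

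For K = 4 and ICC 0.05:

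- r = 0.05/0.95 = 0.0526
- V0 = 0.1167
- V1 = 0.1167 + 0.75 x 0.0526 = 0.1561
- f = 1 + 15 x 0.0526/74 = 1.011
- critical value: 1.666 x sqrt(0.1167 x 1.011/0.1561) = 1.448 on 74 df, which gives 15.2%

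| Assumed ICC | K = 4 | K = 5 |
|---|---|---|
| 0 | 10.0% | 10.0% |
| 0.02 | 12.1% | 12.4% |
| 0.05 | 15.2% | 16.0% |
| 0.10 | 20.2% | 21.8% |

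Simulation with 40,000 trials per setting agrees to within 0.2 percentage points, and the own-cohort contrast stays at about 10% throughout.

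**Step 4: a single shifted cohort.** The non-centrality is d(1 - 1/K)/sqrt(V0), with d in SDs. For K = 4 and d = 0.25 SD it is 0.1875/0.3416 = 0.55, and that dose's rate is 15.0%; each other dose's is 10.6%. For d = 0.5 SD the rates are 29.2% and 12.2%. For K = 5 and d = 0.5 SD they are 33.6% and 11.6%.

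**Step 5: precision.** The pooled standard error is sqrt(1/15 + 1/20) = 0.342 SD for K = 4 and sqrt(1/15 + 1/25) = 0.327 SD for K = 5. Against concurrent placebo it is sqrt(1/15 + 1/5) = 0.516 SD, which is 1.51 and 1.58 times larger. The approximate 90% half-widths (1.645 x SE) are 0.56 and 0.54 SD pooled, and 0.85 SD within cohort.

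**The case against.** Pooling placebo over cohorts is declared in both documents and gains precision when each cohort has only five placebo women. The protocol names no primary hypothesis test (section 11), calls the efficacy analysis primarily descriptive (11.3.4), and includes placebo mainly as a safety reference (11.1). The ECG modelling in SAP 8.11.7 is itself optional. Entry limits are the same in every cohort, and the outcomes are within-woman changes adjusted for baseline, which removes cohort differences that act through baseline. The permission to adjust assessment timing is only a permission. The one cohort-specific sampling difference found, the 48- and 72-hour PK samples from Cohort 3 (SAP 4.9), falls after the last diary, device, LH and ECG readings. Subject-level listings and the randomisation allocation would allow inspection by cohort.

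Most of this stands, and it limits the severity. It does not remove the point. Baseline adjustment does not touch a difference in placebo response, season or site mix, and listings are not a planned check.

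A reader might infer three stronger things that the documents do not support:

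- **That the error rate is above 10%.** It is 10% if cohorts do not differ, and nothing in the documents says how much they do.
- **That every model is affected in this way.** The exposure-response QTcF model in 8.11.7 uses concentration and one active-or-placebo factor over all cohorts. It also lacks a cohort term, but it does not compare one cohort's active women with pooled placebo.
- **That pooling creates the high chance of some false dose finding.** With four cohorts that chance is already about 30% at ICC 0, because multiplicity is openly left uncontrolled. It rises to about 46% at ICC 0.05.

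**Conclusion.** The concern holds in conditional form. Each dose contrast rests on an unstated and unchecked assumption that cohorts do not differ in mean change after baseline adjustment. If the assumption fails, 75% (four cohorts) or 80% (five) of a cohort-wide shift is credited to that dose, and the per-contrast error rate rises to about 12%, 15-16% or 20-22% at assumed ICCs of 0.02, 0.05 and 0.10. If it is true, the stated 10% is right.

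The shares also assume that each dose is given in one cohort. Protocol 9.2 and 10.7 allow a later cohort to repeat an earlier dose. With equal numbers, a shift in one of that dose's two cohorts would then be credited at 1/2 - 1/K: 25% for four cohorts, 30% for five.

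The documents state no dose-selection rule based on these contrasts, so an effect on later dose choice would be inference. What is missing is a planned way to tell a cohort shift from a dose effect. Since the concurrent placebo data are already collected, adding one is a worthwhile low-cost improvement to exploratory analyses.

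**What to change.** Keep pooled placebo as the main analysis, and add to the SAP:

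1. In 8.10.1.1, 8.10.2.1 and 8.10.4 (and so in the sections that refer to them, including 8.10.3), and in the by-timepoint model of 8.11.7: a pre-specified sensitivity contrast of each dose against its own cohort's placebo, fitted with cohort as a fixed effect and shown in the same table as the pooled contrast.
2. In 8.1: placebo summarised by cohort as well as combined.
3. A reporting rule: a dose-specific or dose-ordering finding whose direction is not supported against concurrent placebo will be reported as possibly due to cohort differences.

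A random cohort effect may be a further sensitivity model, but should not be presented as a full correction. With four cohorts and an ICC of 0.05, a truncated moment estimate of the cohort variance is zero in about half of trials. With residual degrees of freedom, an error rate of about 13% remains; a Satterthwaite-type approximation brought it to about 11%.

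The cost is a few extra outputs and no new data. The limitation is precision: the own-cohort contrast has a standard error of about 0.52 SD and rests on five placebo women. It should therefore be read for direction and gross disagreement with the pooled result; failing to reach significance on it should not be a reason to discard a finding.

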8.10.1.2 Hot Flashes Average Severity

Severity by day

Daily (24-hour) hot flashes average severity for Day Y will be equal to the (number of mild hot flashes recorded on Day Y + number of moderate hot flashes recorded on Day Y x 2 + number of severe hot flashes recorded on Day Y x 3) / total number of hot flashes recorded on Day Y. As

the hot flashes are recorded twice daily, the number of hot flashes recorded on Day Y is equal to the sum of the Day Y day time hot flushes recorded in the evening + night time hot flushes recorded following morning.

The daily hot flashes average severity will be summarized and displayed graphically (Day -8 onwards) for each day.

Average daily severity by week

The average daily hot flashes severity for each of Week -1, Week 1, and Week 2 will be equal to the average of the daily hot flashes average severity from Day -8 to Day -2 inclusive, from Day 1 to Day 7 inclusive, and from Day 8 to Day 14 inclusive, respectively. The average hot flashes severity by week and the change from Week -1 (for Week 1 and Week 2) will be summarized by treatment.

The same statistical analyses as described in Section 8.10.1.1 will be done for the average daily severity by week and change from Week -1 in hot flashes average severity.

8.10.1.3 Hot Flashes Severity Score

Severity score by day

The hot flashes severity score for Day Y will be equal to the number of mild hot flashes recorded on Day Y + number of moderate hot flashes recorded on Day Y x 2 + number of severe hot flashes recorded on Day Y x 3. As the hot flashes are recorded twice daily, the number of hot flashes recorded on Day Y is equal to the sum of the Day Y (day time hot flushes recorded in the evening + night time hot flushes recorded following morning).

The daily hot flashes severity score will be summarized and displayed graphically (Day -8 onwards) for each day.

Average daily severity score by week

The average daily hot flashes severity score for each of Week -1, Week 1, and Week 2 will be equal to the average of the daily hot flashes average severity scores from Day -8 to Day -2 inclusive, from Day 1 to Day 7 inclusive, and from Day 8 to Day 14 inclusive, respectively. The daily average hot flashes severity scores by week and the change from Week -1 (for Week 1 and Week 2) will be summarized descriptively by treatment.

The same statistical analyses as described in Section 8.10.1.1 will be done for the average change in severity score from Week -1 hot flashes severity score.

8.10.1.4 Night Time Awakenings

8.10.1.4.1 Night Time Awakenings Secondary to Hot Flashes

The number of NTA secondary to hot flashes will be the sum of the number of moderate and severe night time hot flashes recorded the following morning.

The NTA secondary to hot flashes will be summarized for each day and displayed graphically by day.

The average daily NTA secondary to hot flashes by week for each of Week -1, Week 1, and Week 2 will be equal to the average of the number of NTA secondary to hot flashes per day from Day -8 to Day -2 inclusive, from Day 1 to Day 7 inclusive, and from Day 8 to Day 14 inclusive, respectively. The weekly average number of NTA secondary to hot flashes per day and change from Week -1 will be summarized by treatment.

The same statistical analyses as described in Section 8.10.1.1 will be done for the weekly average change from Week -1 NTA secondary to hot flashes.

8.10.1.4.2 Night Time Awakenings – Total

The total number of night time awakenings for Day Y will be equal to the number of NTA recorded the following morning.

The total NTA will be summarized for each day and displayed graphically by day.

The weekly average NTA per day for each of Week -1, Week 1, and Week 2 will be equal to the average of the number of NTA per day from Day -8 to Day -2 inclusive, from Day 1 to Day 7 inclusive, and from Day 8 to Day 14 inclusive, respectively. The weekly average number of NTA per day and change from Week -1 will be summarized by treatment.

The same statistical analyses as described in section 8.10.1.1 will be done for the weekly average change from Week -1 NTA.

8.10.2 Continuous Hot Flash Diary

8.10.2.1 Frequency of Hot Flashes

Frequency by day

Daily (24-hour) frequency of hot flashes for Day Y for the continuous hot flash diary will be equal to the number of hot flashes recorded on Day Y (day period + night period)

The daily frequency of mild, moderate, severe, moderate/severe, and total hot flashes as measured by continuous day-time diary will be summarized for each day. The mean (+SE) in frequency of mild, moderate, severe, moderate/severe, and total hot flashes will be displayed graphically by day. The change from Day -1 will also be summarized.

Average daily frequency by week

The average daily frequency of hot flashes for Week 1 will be equal to the average of the daily frequency of hot flashes from Day 1 to Day 7, inclusive.

The Week 1 average frequency of mild, moderate, severe, moderate to severe, and total hot flashes will be summarized by treatment.

Statistical analysis

The analysis will test the treatment difference of daily frequency of moderate/severe hot flashes from Day -1 to Day 7 and Day 14.

The analysis will be based on a linear mixed-effects model with the change from Day -1 as a dependent variable, treatment, day and treatment-by-day interaction as fixed effects, subject as a random effect, and the number of moderate/severe hot flashes at Day -1 and the interaction with day as covariates. Subjects dosed with placebo will be analyzed as a pooled group. An unstructured covariance matrix will be specified for the repeated measures at postdose timepoints for each subject. From this analysis, the LS mean and 2-sided 90 % CIs will be calculated for the contrast “NT-814 versus placebo” at each treatment and each postdose day, separately.

Following is the SAS code for reference:

```
proc mixed data=dataset ;  
class TRT <50 mg NT-814, 100 mg NT-814, 150 mg NT-814, etc..., placebo> DAY <7,14> USUBJID;  
model CHG = TRT DAY TRT*DAY BSL BSL*DAY / s ddfm=kr;  
random USUBJID;  
repeated DAY / type=un subject=USUBJID;  
lsmeans TRT*DAY / cl diff alpha=0.1;  
run;
```

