8.10.2.2 Night Time Awakenings

8.10.2.2.1 Night Time Awakenings Secondary to Hot Flashes

Night time awakenings secondary to hot flashes for Day Y = the sum of the number of moderate and severe night time hot flashes recorded on the continuous diary (as these are defined as resulting in a night time awakening) .

Frequency by day

The NTA secondary to hot flashes will be summarized for each day and displayed graphically by day. The change from Day -1 will also be summarized.

Average daily frequency by week

The average daily NTA secondary to hot flashes for Week 1 will be equal to the average of the NTA from Day 1 to Day 7. The average daily NTA secondary to hot flashes for Week 1 will be summarized by treatment.

The same statistical analyses for the daily scores as described in section 8.10.2.1 will be done based on the change from Day -1 NTA.

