8.10.3 Sternal Skin Conductance Monitors

Frequency by day

The Day -1 frequency of hot flashes will be the number of hot flashes detected by the device from 24 hours before dosing on Day 1 to the dosing on Day 1. If there is >24 hours of recorded data, then only the 24-hour prior to the time of dosing on Day 1 will be used. If there is <24 hours of data recorded, then all the recorded data will be used and the actual recording duration will be used to derive a 24 hour value.

Postbaseline values will be based on 24-hour periods from the dose time on Day 1. If the recording time on Day 7 (or an earlier day in the event of early withdrawal) is <24 hours, then all the recorded data will be used and the actual recording duration will be used to derive a 24-hour value.

The number of algorithm-detected hot flashes (Bahr et al *Physiol Meas.* 2014 February ; 35(2): 95–110. doi:10.1088/0967-3334/35/2/95; algorithm commercial property of SimplexScientific LLC) will be summarized and displayed graphically for each day by treatment. The change from Day -1 will also be summarized.

Average daily frequency by week

The average daily frequency of hot flashes detected by the device for Week 1 will be equal to the average of the daily frequency of hot flashes detected by the device from Day 1 to Day 7 inclusive.

The average daily frequency for Week 1 will be summarized by treatment.

Statistical analysis

The same statistical analyses as described in Section 8.10.2.1 will be done for the change from Day -1 in the frequency of hot flashes detected by the device.

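### Skin-conductance hot flash counts are compared with placebo on Day 7 and Day 14 only; an averaged contrast (Days 5–7, and Week 1) should be added in SAP 8.10.3

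*SAP*

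**What the plan says.** SAP 8.10.3 counts device-detected flashes in 24-hour periods from the Day 1 dose, with the 24 hours before that dose as the Day -1 value. It averages Days 1 to 7 into a Week 1 figure, used as follows: "The average daily frequency for Week 1 will be summarized by treatment". For inference, 8.10.3 refers to the analysis in 8.10.2.1, applied to the change from Day -1.

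That model is explicit about its days: "The analysis will test the treatment difference of daily frequency of moderate/severe hot flashes from Day -1 to Day 7 and Day 14". The reference code agrees, with the class levels "DAY <7,14> USUBJID". The continuous diary's weekly average is also descriptive only: "The Week 1 average frequency of mild, moderate, severe, moderate to severe, and total hot flashes will be summarized by treatment". Night-time awakenings in that diary follow the same pattern (8.10.2.2.1): "The average daily NTA secondary to hot flashes for Week 1 will be summarized by treatment".

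The table list in SAP 9 matches. Table 14.2.3.2, the monitor by week, is a summary. Table 14.2.3.3, the statistical analysis, covers daily frequency.

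The twice-daily diary is treated differently: 8.10.1.1 models the change from Week -1 to the Week 1 and Week 2 averages. For all efficacy analyses, "Any statistical hypothesis tests and/or CIs will be two-sided, using a type I error rate of 0.1" (SAP 8.10).

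**The concern.** A single day's count carries the full day-to-day variation of a woman's flashes. The Day 7 contrast sets one such count against another single-day count, Day -1, in 15 active women per dose and 20 to 25 pooled placebo women (5 per cohort, four or five cohorts). Six further post-dose days from the same device are already derived but inform no comparison with placebo.

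This matters most for the monitor. Protocol 10.2.3 and SAP 4.8.2 justify it on the ground that women under-report flashes in diaries, so a diary result is not a full substitute. Its endpoint (Protocol 8.3, SAP 3.5) is change from Day -1 with no post-dose day named, so nothing in the protocol confines the comparison to Day 7 and Day 14.

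A single day is also easily lost. Under SAP 8.2 a recording gap makes the whole day missing, which removes that woman's Day 7 value. A weekly value needs only four complete days.

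**Working it through.** **No stated figure to reproduce.** The documents give no power, SD or effect size for any hot flash comparison. The one power statement (SAP 8.12) concerns AUC0-24 between dose levels and does not bear on this point.

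**Inputs from the documents:** Day -1 value as covariate and Days 7 and 14 as tested days (8.10.2.1); Week 1 = Days 1–7 (8.10.3); 15 active and 5 placebo per cohort (4.1), placebo pooled (8.1); two-sided 0.1 (8.10).

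**Assumptions, not in the documents:** every day has variance s²; any two post-dose days correlate r; Day -1 and any post-dose day correlate b.

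**Formula.** The mean of k post-dose days has variance s²[1+(k−1)r]/k and covariance b·s² with Day -1. Adjusted for Day -1, its residual variance is s²{[1+(k−1)r]/k − b²}. For one day it is s²(1−b²). So:

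variance ratio = {[1+(k−1)r]/k − b²} / (1−b²); SE ratio = its square root.

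The ratio does not depend on sample size or allocation. With Day -1 as covariate, modelling the change or the level gives the same contrast.

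**Worked case,** b = r = 0.5:
- Week 1 (k=7): (4/7 − 0.25)/0.75 = 0.429; SE ratio 0.65.
- Days 5–7 (k=3): (2/3 − 0.25)/0.75 = 0.556; SE ratio 0.75.

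| b | r | Week 1: variance ratio | SE ratio | Days 5–7: variance ratio | SE ratio |
|---|---|---|---|---|---|
| 0.5 | 0.5 | 0.429 | 0.65 | 0.556 | 0.75 |
| 0.7 | 0.7 | 0.496 | 0.70 | 0.608 | 0.78 |
| 0.5 | 0.7 | 0.657 | 0.81 | 0.733 | 0.86 |
| 0.5 | 0.8 | 0.771 | 0.88 | 0.822 | 0.91 |
| 0.5 | 0.9 | 0.886 | 0.94 | 0.911 | 0.95 |

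The SE therefore falls 30–35% (Week 1) and 22–25% (Days 5–7) in the first two rows, and 6–19% and 5–14% in the last three.

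**Interval width.** The 90% half-width for 15 v 20, in units of s, is 1.645 × √[residual variance × (1/15 + 1/20)]:
- b = r = 0.5: residual variances 0.750 (Day 7), 0.417 (Days 5–7), 0.321 (Week 1) give 0.49, 0.36 and 0.32.
- b = r = 0.7: 0.510, 0.310 and 0.253 give 0.40, 0.31 and 0.28.

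**Dilution.** Let f be the effect in the average divided by the effect on Day 7. The average has the larger signal-to-noise ratio only if f exceeds the SE ratio. For Week 1 that threshold is 0.65–0.70 at equal correlation and 0.81–0.94 in the less favourable rows; for Days 5–7 it is 0.75–0.78 and 0.86–0.95.
- Effect rising linearly to full by Day 5: Week 1 f = (0.2+0.4+0.6+0.8+1+1+1)/7 = 0.71; Days 5–7 f = 1. Week 1 is barely ahead at equal correlation and behind otherwise. Days 5–7 is ahead in every row.
- Rising linearly to full by Day 7: Week 1 f = 28/49 = 0.57, behind in every row. Days 5–7 f = 18/21 = 0.86, ahead at equal correlation, about level at b = 0.5, r = 0.7, and behind at r = 0.8–0.9.

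**The case against.** **The SAP follows the protocol.** For the continuous diary this stands. Protocol 8.3 defines that endpoint as change from Day -1 to Day 7 and Day 14, and the model tests those days. A reader might infer that the diary analysis departs from the protocol or has the same gap; it does not. The twice-daily diary already gives a modelled Week 1 contrast for moderate/severe frequency (8.10.1.1) and for awakenings due to flashes (8.10.1.4.1), in the same women on the same days.

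**The Week 1 average is a different quantity.** It also stands that this average describes the effect during accumulation. Protocol 5.5 predicts steady state over the first 7 days of dosing, so early days may dilute the effect. A reader might infer a specific rise in power from averaging. That would need the full effect from Day 1, which the documents do not support, and the dilution figures above show that the gain can vanish or reverse.

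**The monitor is not the only objective measure.** Correct: LH AUC0-8 is listed among the efficacy assessments and is modelled against pooled placebo (8.10.4). The monitor is the only objective count of flashes.

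**Everything here is exploratory.** Also correct. The protocol pre-specifies no primary hypothesis test, and efficacy is primarily descriptive. Each monitored day, including Days 1–6, is summarised by treatment with change from Day -1 and plotted. The data are not hidden, and no planned result is invalid.

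None of this explains why the monitor, with no post-dose day fixed by its endpoint, has no averaged contrast.

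**Conclusion.** The point holds for the monitor in SAP 8.10.3. Its placebo comparison uses single days although adjacent days are recorded and a weekly average is derived. The consequence is lost precision in an exploratory analysis.

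The size rests wholly on assumed correlations and equal daily variances. At one end, averaging narrows the interval by about a third; at the other, by about a twentieth. These figures concern precision, not power. They cannot be tied to device counts, because the documents give no variance for them; the eligibility range of 7–20 a day refers to diary-reported moderate to severe flashes.

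Of the two averages, Days 5–7 is the sturdier: it gains less precision but is less exposed to the days before steady state. Day 14 is one recorded day and cannot be averaged.

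**What to change.** In SAP 8.10.3, keep the Day 7 and Day 14 contrasts. Before unblinding, add an exploratory ANCOVA of the change from Day -1 to (a) the Days 5–7 average and (b) the Week 1 average, with treatment and the Day -1 value in the model and 90% CIs for each dose against pooled placebo.

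State a completeness rule for (a), for example at least 2 of 3 complete days, because the four-day rule in 8.2 cannot apply to three days. Use the existing four-day rule for (b). Add a matching statistical-analysis table beside 14.2.3.3. Report (b) as an average over accumulation, not as a steady-state effect.

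The same may be done for the continuous diary for consistency, but it is less needed there.

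The cost is a few model runs on data already collected, plus 8 to 10 further unadjusted contrasts (two averages × four or five doses). If the continuous diary's flash frequency and its awakenings due to flashes were included, the total would be 24 to 30, which is a reason to limit the addition to the monitor.
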